#### **1.4 Preliminary Studies**

We have performed significant preliminary research into optimizing each of the necessary steps for clinical implementation of the Scan-Plan-Treat STAT RT workflow as detailed below. Preliminary clinical data will be collected from patients treated with STAT RT on this protocol to optimize the software required to develop the more efficient Scan-Plan-Treat STAT RT workflow. A Scan-Plan-Treat workflow will not be used on this clinical protocol.

##### **1. Preliminary Clinical Outcomes of Patients Treated with STAT RT**

We have treated approximately 30 cancer patients with a conformal hypofractionated STAT RT treatment regimen for a variety of palliative indications. We have treated patients with IMRT and 3D TomoTherapy planning modes and have extensive experience using the TomoTherapy planning systems for optimizing conformality of the radiation. Retrospective review of these patients shows that the majority of them have had rapid and durable palliation of symptoms with minimal toxicity (unpublished data). In general, patients are extremely satisfied with the speed at which their treatment is initiated and the convenience of the hypofractionated regimens.

##### **2. Preliminary Studies for Scan-Plan-Treat STAT RT implementation**

###### **a) New image co-registration workflow**

FDA-approved imaging software for rigid and deformable co-registration and transference of target and OAR contours from diagnostic image sets to either kVCT or MVCT images is commercially available. We are using Velocity® image processing software. Our preliminary unpublished data confirms that the MVCT scan has sufficient resolution, particularly of bone anatomy, for accurate co-registration to contoured diagnostic images and that this one step co-registration process yields comparable agreement to the conventional two step image co-registration workflow with +/- 2-3 mm differences. **See Figure 4.** This level of agreement is consistent with results reported from image co-registration studies performed on a multi-institutional pediatric clinical trial with co-registration data of 51 patients from 45 institutions using 11 different image software systems. They reported an inherent uncertainty of 2 mm for MRI to CT co-registration (55). MVCT image guidance scans and kVCT simulation co-registration occurs routinely in the clinic and only takes a few seconds, therefore,

we do not believe that this will be a rate limiting step in the clinical implementation of the Scan-Plan-Treat STAT RT workflow.

**b) Rapid inverse treatment planning on MVCT scans**

We have shown that accelerated treatment planning software for Helical TomoTherapy provides clinically acceptable dosimetry, with conformality and homogeneity that is superior to standard LINAC-based 3D conformal planning and is only slightly inferior to standard Helical TomoTherapy dosimetry (33). We have also shown that, with planning times of 2-5 minutes, this accelerated treatment planning software provides levels of dosimetric conformality, heterogeneity, and avoidance of organs at risk for simple SBRT treatments that are clinically equivalent to those generated with conventional Helical TomoTherapy treatment planning(39). This preliminary data supports that treatment planning speed is not likely to be rate limiting in the ultimate clinical implementation of the Scan-Plan-Treat STAT RT workflow.

**c) Monte Carlo secondary dose calculation**

We have clinically implemented a validated software second dose calculation check that reads TomoTherapy treatment plan information exported through DICOM and then performs a Monte Carlo dose calculation in a few minutes. Our preliminary results show a 3D-dose distribution can be calculated within 2-5 minutes (56). The software has been used clinically for 8 months on all patients treated on TomoTherapy at UVA with excellence results.

**d) Novel CT-detector-based quality assurance methodology**

Our pre-clinical evaluation of the CT-detector based exit radiation dose verification algorithm has been retrospectively studied by Sheng et al using in-development software (53). We compared with planned and delivered doses with the conventional phantom quality assurance measurements for 24 patients and 347 treatment fractions. The concordance of planned to delivered dose calculated by the in-development software was shown to be  $\pm 5\%$  (53). This tolerance is within the standard of care of other current clinically available quality assurance methods. We are also using the CT detector exit dose data to measure the MLC leaf opening time and comparing this with the calculated leaf opening time as a novel quality assurance methodology.

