### **5. Novel CT-detector-based quality assurance methodology**

Current standard of care TomoTherapy quality assurance methodology requires that each patient-specific treatment plan be delivered to a cylindrical plastic phantom with ion chamber and film measurement or an array of radiation detectors to ensure geometric and dose accuracy to within  $\pm 3\%$ . However, this method does not measure the dose that the patient is receiving during treatment or provide full 3D dose verification. It causes another delay in delivering the first treatment to the patient as it requires approximately 30-40 minutes to complete, and is generally done by a medical physicist after clinical patient care is finished. A methodology to monitor the patient exit dose in real time would increase patient safety through verification of daily treatment accuracy as well as expedite the treatment workflow. Clearly, a real-time quality assurance methodology that does not require moving the patient off the TomoTherapy treatment couch for phantom measurements is essential for the development of a 30-minute Scan-Plan-Treat workflow. Current dose verification methodologies measuring dose at the time of patient treatment are limited to point measurements on the patient surface (44), which is rarely in the target volume or a critical OAR, or though

expensive implanted dosimeters (45, 46) which are not practical for most palliative patients. Since there is not a method to directly measure the three dimensional dose in the patient, alternative approaches are being developed and tested in academic clinical settings. These alternative approaches reconstruct the delivered three dimensional dose distribution based on the measurement of either entrance or exit dose and back-projecting the measurements onto simulation or image guidance CT image sets.

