The opportunity to reconstruct dose from information collected during treatment became available with the incorporation of radiation imaging detectors, such as electronic portal imaging devices (EPID) on linear-accelerators and CT detector arrays on TomoTherapy. Dose reconstruction using in-line EPID was first described by McNutt et al (47, 48). The EPID, when deployed during treatment, collects exit fluence from the patient and then back-projects this to X-ray fluence before entering the patient; then, the dose in the patient is re-computed using this entrance fluence and the planning CT images. However, there are many limitations to EPID-based dose verification. For example, the EPID was originally designed for semi-quantitative portal imaging; and for the purpose of dose reconstruction, it suffers from a narrow dynamic range, short life span, non-linearity in the dose response, ghost artifacts from low temporal resolution, and cross-plane scatter photon contribution to the measured fluence (49). Investigators are currently working on methods to overcome these challenges.

The TomoTherapy unit has an in-line source-patient-detector geometry with CT ion chamber detectors that are used for daily MVCT scan image guidance for accurate patient positioning that remain in place during both imaging and treatment. **See Figure 3**. These CT detectors can also be used to measure the patient exit dose fluence and back-project this onto a planning CT scan for volumetric or 3D dose reconstruction. Dose verification on TomoTherapy was first studied by Kapatoes et al., who calculated the entrance fluence from the exit dose using a transfer matrix, which is calculated based on the radiological path length from the source to the detector (50, 51). The use of a CT ion chamber array has multiple advantages over EPID for exit fluence measurement. It is more durable, and has a much longer life span. It has a wider dynamic range and doesn't limit treatment positions. Finally, it is less sensitive to the noise from cross-plane scatter photons that complicate EPID-based dose reconstruction (52). Our recently published preliminary data showed that the current TomoTherapy CT-detector based algorithm for dose reconstruction is robust with +/- 3-5% accuracy which is well within the acceptable range for clinical care (53). We will collect clinical data and continue to optimize this in-development software.

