### **4.2 Treatment Dosage and Administration: Radiation Therapy**

- Approved and consented patients will receive radiotherapy using the STAT RT workflow.
- The patients will receive Helical TomoTherapy using the Hi Art system (TomoTherapy Inc).
- Patients will receive a total of 2-5 fractions of high dose palliative radiation therapy consisting of 5-10 Gy per fraction with a minimum biologic effective dose (BED) of 25 Gy.

- **Dose specifications:** The planning target volume (PTV) will be prescribed a minimum BED of 25 Gy. The maximum dose prescribed will be a BED of 72 Gy.
- **Variations of dose prescription:** There is a wide acceptable range of doses delivered to bone metastases in the palliative setting. The appropriate dose will be determined by tumor histology (whether the tumor is radiosensitive or radioresistant) and location of critical structures (to prevent radiation-induced toxicity to adjacent organs at risk). Dose prescription will be at the discretion of the treating radiation oncologist, however will have to be at least a BED= 25 Gy.
  - **Beam Energy** 6 MV (TomoTherapy only has one beam energy)
  - **Beam Shaping** All treatments will be delivered with conformal delivery with multi-leaf collimator beam modulation.
- **Localization, Simulation and Immobilization:** All patients will undergo non-contrast enhanced kVCT simulations with standard immobilization devices: aquaplast masks for head, neck, upper thoracic PTVs, Vac-Lok cushions or custom headrests, body-fix immobilization system for spinal tumors are all permissible. Diagnostic contrast enhanced CT scans, PET CT scans, or MRIs from the patient's PACS chart will be used to guide target and OAR contouring. The diagnostic images will be rigidly (MRI, contrast enhanced CT, PET CT) or deformably (contrast enhanced CT, PET CT) co-registered to the kVCT simulation in Velocity. Following contour transfer to the kVCT simulation image set, the images will be reviewed and approved by a physician and then transferred to the TomoTherapy treatment planning station.
- An experimental contouring plan will be created to compare to the conventional treatment plan but will not be used in treatment planning. We will experimentally co-register the contoured diagnostic images directly to the MVCT scan and generate the PTV and OAR contours using only the MVCT scan without the kVCT intermediate. Contours generated by both methods will then be compared.

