**c) Exit Radiation Dose Verification**

In-development software provided by TomoTherapy Inc.® will be used to measure the exit dose fluence, backproject this fluence as entrance fluence, and then calculate the patient dose on the MVCT scan. This software will be further optimized and refined on this clinical trial. All patients' radiation treatment plans will undergo standard of care phantom-based quality assurance measurements. The phantom exit dose will also be calculated via this software in this optimization process. By comparing the values obtained with the software to the calculated treatment plan and phantom measurements, we hope to optimize this novel radiation dose verification software to +/- 3% calculated to delivered dose. Preliminary data shows that we are already at +/- 5% calculated to delivered dose (53).

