### **7.3 Data Analyses Plans**

Treatment response as defined by International Bone Metastases Consensus Group will be determined for each patient. As described in Section 6.1.1, pain intensity as defined by the BPI and opiate use as quantified by the OMED will be used to categorize patients as having: Complete Response, Partial Response, Pain Progression, Stable Pain. At each evaluation, the patient's BPI and OMED at that visit will be compared to the pre-treatment levels. The "Worst Pain" score from the patient's BPI will be used to evaluate for treatment response. Patient response does not require a statistical analysis. The percentage of patients in each response category at each evaluation will be reported.

Patient pain will be recorded using the BPI before treatment and at designated evaluations after treatment. Pain scores before and after treatment will be compared using a Wilcoxon signed ranks test to determine if there is a statistically significant difference. Example: Pre-treatment vs. 1 week, Pre-treatment vs. 4 weeks, etc.

Analgesic use will be recorded by requiring each patient to keep a logbook of their analgesic intake. Their opiate intake for the last 72 hours will be converted to OMED at each evaluation and used in the categorization of treatment response. The difference between their OMED before and after treatment will be compared using paired two-sample t-tests.

Patients' functional status will be determined using the Karnofsky Performance Scale at each evaluation. The difference between the KPS before and after treatment will be compared using a Wilcoxon signed ranks test.

Patients' quality of life will be measured using FACT-BP and FACT-G scores at each evaluation. The difference between the FACT scores before and after treatment will be compared using a Wilcoxon signed ranks test.

Patient satisfaction will be measured using a modified version of FACT - TS – BTCSQ. No statistical analysis will be required for reporting the results. The average scores from the satisfaction survey will be reported.

To evaluate the CT detector dose calculations, the delivered radiation dose obtained using the phantom quality assurance will be compared to the exit radiation dose quality assurance calculation. The calculated dose and delivered dose for each patient will be compared using a paired two-sample t-test, and the % difference in dose will be reported.

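### The ±5% baseline and ±3% goal for the exit-dose software have no stated unit or statistic, and the per-patient t-test cannot show whether individual deliveries fall within ±3%

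*Combined protocol and SAP*

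**What the plan says.** The starting figure is in Section 1.4, item 2 d). Planned and delivered doses were compared with phantom "quality assurance measurements for 24 patients and 347 treatment fractions". The result follows: "The concordance of planned to delivered dose calculated by the in-development software was shown to be" ±5%. The text does not say whether this describes a fraction or a patient, or whether it is a standard deviation, a 95% limit or a range. Section 1.3.9, item 5, gives ±3-5% for the same cited source.

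Section 7.1, 2) c) uses ±5% as the current position and states the goal: "we hope to optimize this novel radiation dose verification software to +/- 3% calculated to delivered dose". Again no unit or statistic is given.

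The only planned analysis is in Section 7.3. The phantom-measured dose is to be set against the exit-dose calculation, and then: "The calculated dose and delivered dose for each patient will be compared using a paired two-sample t-test", with the percentage difference reported. How a patient's single value is formed is not described.

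On purpose, Section 1.3.9, item 5, says that real-time exit-dose monitoring "would increase patient safety through verification of daily treatment accuracy". Section 1.5 adds that, if the two methods prove equivalent, the site could in future rely on the detector and software alone.

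On the data available, Section 4.2 states: "Patients will receive a total of 2-5 fractions of high dose palliative radiation therapy". The patient may have 1-3 targets (Section 3.1.3). The Time and Events Table (Section 5.1) puts quality assurance before treatment and exit-dose verification during treatment.

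**The concern.** The claim being prepared is about single deliveries: that the software can confirm, on the day, that the dose was right. The planned test addresses whether the average difference across patients is zero. Large errors of opposite sign satisfy that test, and neither the test nor one percentage per patient reveals how often a delivery falls outside ±3%.

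A second difficulty lies in measuring progress from ±5% to ±3%. A spread depends on how many readings are combined in each value. If the preliminary and trial figures combine different numbers of fractions, the spread can change although the software has not. The documents do not say what either figure combines, so neither the size nor the direction of that change is known.

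At stake is the reading of Objective 2.2.1, and any later argument for dropping phantom measurement that rests on it. The primary clinical outcomes are not affected.

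**Working it through.** **Inputs from the documents.** 24 patients and 347 fractions (Section 1.4); ±5% now and ±3% as the goal (Section 7.1 c); 2-5 fractions per patient (Section 4.2), most expected to have 2-3 (Section 1.3.4).

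**Inputs assumed.** The within-patient correlation of fraction errors, ρ, is not in the documents, so it is varied from 0 to 1. Fractions are taken as equal in dose. The ±5% itself cannot be reproduced, because no standard deviation, coverage level or per-fraction data are given.

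**Step 1: what the t-test sees.** If half the patients are at +5% and half at -5%, the mean difference is 0% and the test finds nothing, although every value lies outside ±3%. This does not depend on how the patient value is built. If that value does combine fractions, the same offset occurs within a patient: (+5% - 5%)/2 = 0%.

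**Step 2: if ±5% is a per-fraction limit.** With unchanged software, the limit for a mean of k fractions is 5% × √[ρ + (1-ρ)/k].

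| ρ | k = 2 | k = 3 | k = 5 |
|---|---|---|---|
| 0 | ±3.54% | ±2.89% | ±2.24% |
| 0.5 | ±4.33% | ±4.08% | ±3.87% |
| 1 | ±5.00% | ±5.00% | ±5.00% |

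For the limit to reach ±3%, ρ + (1-ρ)/k must be at most (3/5)² = 0.36, that is, ρ ≤ (0.36 - 1/k)/(1 - 1/k). For k = 3 this gives ρ ≤ 0.04 and for k = 5, ρ ≤ 0.20. For k = 2 the bound is -0.28, so no correlation between 0 and 1 achieves it.

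**Step 3: if ±5% is already a patient mean.** The average is 347/24 = 14.46 fractions per patient. With unchanged software, the limit for k fractions is 5% × √{[ρ + (1-ρ)/k] / [ρ + (1-ρ)/14.46]}. At ρ = 0 this is ±13.4% for k = 2 and ±8.5% for k = 5. At ρ = 0.5 it is ±5.9% and ±5.3%. A real improvement could then be hidden.

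**Step 4: the statistic matters too.** If ±5% is a 95% limit per fraction, the standard deviation is 5/1.96 = 2.55%, and 24% of single fractions lie outside ±3%. For 3-fraction means the share outside is 4% at ρ = 0 and 15% at ρ = 0.5. If ±5% is one standard deviation, 55% of single fractions lie outside ±3%.

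**The case against.** A reader might infer that the ±5% is a single-fraction figure, that the trial will average it over 2-5 fractions, and that averaging alone will therefore deliver the ±3%. The documents support none of these steps. Section 1.4 gives counts of patients and fractions, not the unit of the ±5%. Section 7.3 mentions no averaging, summing or pooling of lesions. Its comparator is the phantom measurement, scheduled only before treatment, and Section 7.1 c) says that exit dose is also calculated for the phantom. The per-patient pair could therefore be one phantom reading against one phantom reconstruction, for which one value per plan is reasonable. Even granting the averaging, ±3% needs nearly independent errors with 3 fractions and is out of reach with 2, and 2-3 is the expected schedule. Section 1.3.9, item 5, also notes that reconstruction depends on knowing the patient's geometry and attenuation, a source of error that could recur across fractions.

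The importance is also limited. This is a secondary, developmental aim in a 30-patient pilot, Objective 2.2.1 has no pass/fail threshold, the ±3% is a hope, and the software replaces no standard check during the trial.

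These points all stand, and they rule out any claim that averaging will manufacture the improvement. They do not supply what is missing. A phantom-only comparison leaves patient deliveries unanalysed, and each of the other readings leaves the agreement of individual daily deliveries unreported.

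**Conclusion.** The concern holds as a gap in definition and analysis. The ±5% and ±3% have no stated unit or statistic, so the plan gives no basis for comparing them. A per-patient test of mean difference cannot show whether individual deliveries fall within ±3%, which is what daily verification requires. This part needs no assumption.

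The size of any distortion is conditional. If ±5% is a per-fraction limit and patient values are means of equal fractions, unchanged software gives anything from ±2.2% (5 fractions, independent errors) to ±5% (fully shared errors). If ±5% is already a mean over about 14.5 fractions, the spread widens at any correlation below 1. The direction is therefore unknown until the unit is stated.

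**What to change.** In Sections 7.1 c) and 7.3:

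- State the unit and the statistic behind both ±5% and ±3%.
- For each patient delivery (fraction and target) with exit-dose data, report the percentage difference of reconstructed from planned dose. Section 4.2 already foresees a comparison with planned dose, and that reference exists for every fraction, whereas phantom quality assurance is scheduled only before treatment.
- Assess ±3% with limits of agreement from a mixed model with a patient random effect, and give the share of fractions within ±3%.
- Report phantom exit dose against phantom measurement separately, once per plan.
- Keep the per-patient course total as a secondary summary.
- Compare with the preliminary ±5% only on the same unit and statistic. If the preliminary data cannot be put in that form, claim no improvement from it.

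The cost is revised wording and a modest extra analysis. Exit dose is already scheduled during treatment, but the documents do not say that it is captured at every fraction, so the number of deliveries with data should be reported. The main downside is that the reported accuracy may look less favourable than a per-patient figure.

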**e) Optical tracking methods for patient intra-fractional motion monitoring**

At the Emily Couric Cancer Center, we have recently developed an in-house optical tracking system using multiple OptiTrack FLEX:V100 cameras (Natural Point, Corvallis, OR). **See Figure 4**. The camera utilizes 26 infrared light-emitting diodes (LEDs) and a charge coupled device (CCD) to capture the reflective light from markers with special coating. By using multiple cameras, the 3D position of each reflective marker can be determined precisely. Three reflective markers are fixed on a rigid body marker base that can vary in size from a few centimeters to much larger and create a “trackable” that can easily be placed on a patient’s surface to track their motion. **See Figure 5**. The x, y, z, yaw, pitch

and roll of the trackable can be detected by the camera system. An in-house C program was developed to stream the data and display the position of the trackable in real time. Multiple trackables can be placed on a patient and monitored simultaneously. In the lab, localization precision of 0.1 mm was achieved (unpublished data). Through strategic positioning of the trackables, movements of the head, neck, and extracranial locations can be closely monitored. This optical tracking technology is unique to ECCCC and is not available at CRH and patients treated at CRH will not undergo this experimental aspect of the trial.

